## 7. Retention of Specimens

Future biomedical research specimens will be stored in the biorepository for potential analysis for up to 20 years from the end of the main study. Specimens may be stored for longer if a regulatory or governmental authority has active questions that are

being answered. In this special circumstance, specimens will be stored until these questions have been adequately addressed.

Specimens from the study site will be shipped to a central laboratory and then shipped to the Sponsor-designated biorepository. If a central laboratory is not utilized in a particular study, the study site will ship directly to the Sponsor-designated biorepository. The specimens will be stored under strict supervision in a limited access facility which operates to assure the integrity of the specimens. Specimens will be destroyed according to Sponsor policies and procedures and this destruction will be documented in the biorepository database.

## **8. Data Security**

Databases containing specimen information and test results are accessible only to the authorized Sponsor representatives and the designated study administrator research personnel and/or collaborators. Database user authentication is highly secure, and is accomplished using network security policies and practices based on international standards to protect against unauthorized access.

## **9. Reporting of Future Biomedical Research Data to Participants**

No information obtained from exploratory laboratory studies will be reported to the participant, family, or physicians. Principle reasons not to inform or return results to the participant include: Lack of relevance to participant health, limitations of predictive capability, and concerns regarding misinterpretation.

If important research findings are discovered, the Sponsor may publish results, present results in national meetings, and make results accessible on a public website in order to rapidly report this information to doctors and participants. Participants will not be identified by name in any published reports about this study or in any other scientific publication or presentation.

## **10. Future Biomedical Research Study Population**

Every effort will be made to recruit all participants diagnosed and treated on Sponsor clinical studies for future biomedical research.

## **11. Risks Versus Benefits of Future Biomedical Research**

For future biomedical research, risks to the participant have been minimized and are described in the Future Biomedical Research informed consent.

The Sponsor has developed strict security, policies, and procedures to address participant data privacy concerns. Data privacy risks are largely limited to rare situations involving possible breach of confidentiality. In this highly unlikely situation, there is risk that the information, like all medical information, may be misused.

## 12. Questions

Any questions related to the future biomedical research should be emailed directly to [[contact]](mailto:[contact]).

## 10.7 Appendix 7: Country-specific Requirements

The information in this appendix is added to the main protocol to describe the Off-treatment Durability Study Period that will be conducted only at certain study sites in the United Kingdom, United States of America, Ukraine, Germany and Poland.

### 1.1 Synopsis

**Study Type:** The Off-treatment Durability Study Period is observational.

[figure not shown]
**Intervention Model:** At selected sites and countries, participants from any treatment group (ie, MK-7264 45 mg BID, MK-7264 15 mg BID, or placebo) who provide written informed consent, may also participate in a 3-month, Off-treatment Durability Study Period.

**Estimated Duration of Study:** The Sponsor estimates that the Off-treatment Durability Study Period will require approximately 16 months from the time the first participant starts the Off-treatment Durability Study Period until the last participant's last study-related telephone call of the Off-treatment Durability Study Period.

**Number of Participants:** Approximately 150 total participants who complete the Main and Extension Study Periods (up to Week 52) of this study and another ongoing, Phase 3 study being conducted by the Sponsor (P027) will be enrolled in the Off-treatment Durability Period of the study in which they are participating. The number of participants enrolled from each study may vary.

**Duration of Participation:** Participants in the Off-treatment Durability Study Period will be in the study for approximately 3 more months after their Week 52 visit.

## 1.2 Schema

\*Note: Visits 10, 12, 14, 15, 16, and 17 will be conducted by telephone. Visit 14 is a safety follow-up after the last dose of study intervention.

BID = twice daily

### 1.3 Schedule of Activities (SoA)

Study Period	Extension/Off-treatment Durability Study Period		Off-treatment Durability Study Period			Disc Durability Period	Notes
		Follow-up					
Visit Number	Visit 13 (Last visit of Extension Study Period and start Durability Study Period)	Visit 14 (TC)	Visit 15 (TC) Month 1	Visit 16 (TC) Month 2	Visit 17 (TC) Month 3		“Off-treatment Durability Study Period” is also referred to as “Durability Period”
Scheduled Day	Day 365	Day 379	Day 393	Day 421	Day 449		
Scheduling Window (Recommended)	±4 days	+7 days	±7 days	±7 days	±7 days		
Scheduled Week	Week 52	Week 54	Week 56	Week 60	Week 64		
Written Informed Consent for Durability Study Period	X						Consent may be obtained at Visit 9 or later, but prior to performing any procedures related to the Durability Period. If obtained prior to Visit 13, consent should be reviewed with the participant at Visit 13.
Inclusion/Exclusion Criteria for Durability Period	X						
Collect/Review Participant Comment Card	X	X	X	X	X	X	During the Durability Period, review of comment card will be conducted during each TC. See Section 8.1.6 below.
Issue/Instruct in use of new Participant Comment Cards for Durability Period	X						
Review Concomitant Medications	X	X					
Review Treatments Used for Cough and any use of ACEI			X	X	X	X	
Study Intervention Accountability	X						
Contact IRT System	X						

Study Period	Extension/Off-treatment Durability Study Period		Off-treatment Durability Study Period				Notes
		Follow-up				Disc Durability Period	“Off-treatment Durability Study Period” is also referred to as “Durability Period”
Visit Number	Visit 13 (Last visit of Extension Study Period and start Durability Study Period)	Visit 14 (TC)	Visit 15 (TC) Month 1	Visit 16 (TC) Month 2	Visit 17 (TC) Month 3		Sections noted below may be referenced in the main body of the protocol (for general information and information about the Main and Extension Study Periods) and in Appendix 7 (information specific to the Durability Period).
Scheduled Day	Day 365	Day 379	Day 393	Day 421	Day 449		
Scheduling Window (Recommended)	±4 days	+7 days	±7 days	±7 days	±7 days		
Scheduled Week	Week 52	Week 54	Week 56	Week 60	Week 64		
Efficacy Procedures							
Activate ePROs	X		X	X	X	X	See Section 8.2.2 below.
CSD	Daily						
Cough Severity VAS	Daily						
LCQ	X		X	X	X	X	
EQ5D-5L	X		X	X	X	X	
PGIC					X	X	
Safety Procedures							
Physical Examination	X						Directed physical exam
Vital Signs	X						
Weight	X						
Hematology & Chemistry	X						
Urinalysis (w/Microscopy)	X						Dipstick performed for ALL participants. Samples are also collected and sent to central laboratory for ALL participants. See Table 8 (Section 10.2 – Appendix 2).
Specialized Urine Collection for Crystal Assay	X						Only if central laboratory urinalysis is positive for crystals and/or unexplained hematuria. See Section 8.3.7 (main body of protocol).
Adverse Event Monitoring	X	X					Spontaneous reports of certain AEs will be collected after V14. See Section 8.4.1 below for AE reporting requirements after V14.

Study Period	Extension/Off-treatment Durability Study Period		Off-treatment Durability Study Period				Notes
		Follow-up				Disc Durability Period	“Off-treatment Durability Study Period” is also referred to as “Durability Period”
Visit Number	Visit 13 (Last visit of Extension Study Period and start Durability Study Period)	Visit 14 (TC)	Visit 15 (TC) Month 1	Visit 16 (TC) Month 2	Visit 17 (TC) Month 3		Sections noted below may be referenced in the main body of the protocol (for general information and information about the Main and Extension Study Periods) and in Appendix 7 (information specific to the Durability Period).
Scheduled Day	Day 365	Day 379	Day 393	Day 421	Day 449		
Scheduling Window (Recommended)	±4 days	+7 days	±7 days	±7 days	±7 days		
Scheduled Week	Week 52	Week 54	Week 56	Week 60	Week 64		
Pharmacodynamics/Biomarkers							
Pharmacokinetic Sample (blood)	X						
AE = adverse event; ACEI = angiotensin converting enzyme inhibitor; CSD = Cough Severity Diary; Disc = discontinuation; ePRO = electronic patient-reported outcome; EQ5D-5L = EuroQoL 5 Version 5L dimensions questionnaire; IRT = interactive response technology; LCQ = Leicester Cough Questionnaire; PGIC = Patient Global Impression of Change; TC = telephone contact; V = visit; VAS = Visual Analog Scale							

## 2.1 Study Rationale

The MK-7264 Phase 3 program is designed primarily to define the efficacy, safety and tolerability of MK-7264, an orally available P2X3 antagonist, for the treatment of refractory or unexplained chronic cough (RCC, UCC). The Phase 3 studies are designed as randomized, parallel treatment for 1 year with either placebo or 1 of 2 MK-7264 dose levels (15 mg BID, 45 mg BID). However, it is currently unknown how participants will respond to cessation of treatment with MK-7264 after 1 year of therapy. Though limited, short-term data from Protocol 012 (the phase 2b dose ranging study with MK-7264) suggests that participants treated with MK-7264 for 12 weeks and observed 14 days after discontinuation of treatment showed a mean cough frequency off-treatment that did not increase compared to baseline (Week 0), suggesting no evidence of immediate rebound cough.

The addition of the Off-treatment Durability Study Period via the proposed amendment is intended to explore the impact of withdrawing MK-7264 therapy in RCC/UCC patients who have been treated for 1 year.

## 3 Hypothesis, Objectives, and Endpoints

Objectives	Endpoints
Exploratory	

Objective: To evaluate the off-treatment durability after 1 year of treatment with MK-7264, over the course of 3 months off treatment

	

Cough Severity VAS

LCQ

CSD

PGIC

EQ5D-5L

Objective: To evaluate the time to “loss of response” in on-treatment responders over the course of 3 months off treatment

	

Time to loss of response based on VAS

Time to loss of response based on CSD

Time to first use of a medication for cough

## 4.1 Overall Design

Approximately 150 total participants, in either this study or P027 at selected sites and countries, will enter an Off-treatment Durability Study Period at their last visit of the Extension Study Period (V13). The duration of this period will be approximately 3 months.

Individual participation in the entire study is expected to be approximately 66 weeks from Screening (Visit 1) through the end of the Off-treatment Durability Study Period (Visit 17).

Specific procedures to be performed during the Off-treatment Durability Period of the study, as well as associated visit windows, are outlined in the SoA above. General information about each procedure is in Section 8 of the main body of the protocol. Information specific to

the Off-treatment Durability Study Period is in various sections of this appendix (eg, Section 6.5 Concomitant Therapy).

The final database lock for this protocol will be conducted after participants have completed, or discontinued prior to the completion of the Extension Study Period. The final database lock will occur independent of enrollment in the Off-treatment Durability Study.

The data from the Off-treatment Durability Study Period will be summarized in a separate report from the Main and Extension Study Period data.

## 5.1 Inclusion Criteria

Participants are eligible to be included in the Off-treatment Durability Study Period only if all of the following additional criteria apply:

1. Participant completed the Main and Extension Study Periods, on study intervention, through the evening prior to Visit 13.
2. Participant completed the baseline, (Visit 2, Day 0) ePRO diaries (ie, LCQ and EQ5D-5L).
3. Participant completed the Visit 13 LCQ.
4. Participant was at least 80% compliant with completion of the Cough Severity VAS throughout all study periods.
5. Participant was at least 80% compliant with taking the study intervention throughout the Main and Extension Study Periods.

## Informed Consent

6. Participant (or legally acceptable representative if applicable) provides written informed consent for the Off-treatment Durability Study Period.

## 5.2 Exclusion Criteria

Participants are excluded from participation in the Off-treatment Durability Study Period if the following criteria apply:

1. Participant is expected to need to take an angiotensin converting enzyme inhibitor during the Off-treatment Durability Study Period.
2. Participant experienced a serious or clinically significant adverse experience which is still present at the time of providing informed consent for the Off-treatment Durability Study Period.

3. Participant has had clinically significant changes in his/her general medical condition since enrolling in P030.

## 6.5 Concomitant Therapy

Between Visit 13 and Visit 14:

Participants must adhere to the guidance parameters (Section 6.5 of main protocol) and exclusion criteria (Section 5.2 of main protocol) regarding use of concomitant therapy until the Visit 14 telephone contact (ie, for approximately the first 2 weeks of the Off-treatment Durability Study Period).

After Visit 14:

- Participants may take medications and use other treatment as needed, with one exception:
  - Participants should continue to refrain from use of angiotensin converting enzyme inhibitors through completion of the Off-treatment Durability Study Period.

### 8.1.5.2 Concomitant Medications

During the Off-treatment Durability Study Period, only the following treatments will be recorded in the eCRF:

- Treatments used for cough, (prescription and over-the-counter) including natural/herbal remedies, lozenges, or drinks that may include an active anti-tussive or expectorant.
- Angiotensin converting enzyme inhibitors

### 8.1.6 Participant Comment Card

Participants will be provided new participant comment cards for use during the Off-treatment Durability Study Period to capture treatments used between scheduled telephone contacts. The participant comment card should be discussed at each telephone contact as outlined in the SoA. Participants will be encouraged to return comment cards to the study site. Instructions will be provided.

Concomitant therapy described above (Section 8.1.5.2) will be entered into the eCRF.

### **8.1.8 Assignment of Treatment/Randomization Number**

Participants in the Off-treatment Durability Study Period will continue with the same treatment/randomization number assigned at study start.

### **8.2.2 Electronic Patient-reported Outcomes**

Participants in the Off-treatment Durability Study Period will continue to complete the following ePRO measures as specified in the Off-treatment Durability Study Period SoA above: CSD, Cough Severity VAS, LCQ, PGIC, and EQ5D-5L.

Participants will be instructed to complete the daily ePRO measures (CSD and Cough Severity VAS) at approximately the same time each day, from the evening of Visit 13 (ie, the last visit of the Extension Period) until the evening before Visit 17 (ie, last visit of the Off-treatment Durability Study Period) or Discontinuation Visit. If a participant fails to complete the CSD and/or Cough Severity VAS ePRO measure(s), the eDiary will allow the participant, based on recall, to complete the measures at any time in the next 24 hours.

Participants will also be asked to complete the visit ePRO measures (LCQ, EQ5D 5L, and/or PGIC) on the day of the telephone visits as outlined in the SoA. If a participant fails to complete any of the visit ePRO measure(s), the eDiary will allow the participant, based on recall, to complete these measures at any time in the next 48 hours. If these visit ePROs are not completed, site personnel may be asked to reactivate visit questionnaires for the participant and the participant may be asked to complete them at a later date.

Electronic PRO measures must be activated as outlined in the SoA. Visit 13, Visit 15, Visit 16, Visit 17 and the Discontinuation visit ePROs are “activated” by entering actual visit/event dates in the vendor portal (Engage).

### **8.4.1 Time Period and Frequency for Collecting AE, SAE, and Other Reportable Safety Event Information**

Between Visit 13 and Visit 14:

For all study participants, including those entering the Off-treatment Durability Study Period, see Section 8.4.1 of the main protocol for information regarding collection of AEs, SAEs, and Other Reportable Safety Event Information through the 14-day safety follow-up contact (Visit 14).

After Visit 14:

For participants in the Off-treatment Durability Study Period, after Visit 14, the following must be reported to the Sponsor within 24 hours of learning of the event:

- Any drug-related SAEs or SAEs considered to be study participation related and brought to the attention of the investigator
- Any drug-related NSAEs brought to the attention of the investigator during the time the participant is active in the Off-treatment Durability Study Period
- Any pregnancy that is brought to the attention of the investigator during the time the participant is active in the Off-treatment Durability Study Period. The pregnancy must be followed to completion/termination. If the pregnancy continues to term, the outcome (health of the infant) must also be reported.

If the investigator elects to submit AEs for non-Merck products, they should be reported to the Marketing Authorization Holder (MAH) for that product or to the health authority according to the institution's policy or local laws and regulations.

## 8.10 Visit Requirements

### Off-treatment Durability Study Period

- Participants must provide written informed consent to participate in the Off-treatment Durability Study Period. (See Sections 8.1.1 and 8.1.1.1 of the main body of the protocol.)
  - Consent may be obtained at Visit 9 or later, but prior to performing any procedures related to the Off-treatment Durability Study Period. If obtained prior to Visit 13, the consent should be reviewed with the participant at Visit 13.
- Participants will begin the 3-month Off-treatment Durability Study Period on the same day as their final clinic visit (Visit 13) of the Extension Study Period.
- Participants will not take study intervention during the Off-treatment Durability Study Period.
- Participants will continue to complete ePROs as outlined in the SoA.
- No additional clinic visits will be required after the final visit of the Extension Study Period (Visit 13).
  - Telephone contacts will occur as specified on the SoA

Participants will be provided with instructions to return their eDiary device to the study site at the end of the Off-treatment Durability Study Period.

## 9 Statistical Analysis Plan

### 9.2 Responsibility for Analyses/In-house Blinding

The Main Period of the phase 3 study will be completed while the Extension Study Period and Off-treatment Durability Study Period are ongoing. Selected members of the Sponsor study team may be unblinded to review the data from the Main Study Period and author a CSR for facilitating regulatory submission.

A final database lock will occur after all participants have completed the Extension Study Period. This database lock will occur independent of enrollment into the Off-treatment Durability Study Period. The data from the Off-treatment Durability Study Period will be summarized in a separate report from the Main and Extension Study Period data.

The investigator site personnel and the participants will be blinded to intervention assignment until the entire study is completed.

### 9.3 Hypotheses/Estimation

No hypothesis will be tested for the Off-treatment Durability Study Period. Point estimates and 95% confidence intervals (as appropriate) will be provided for the efficacy and safety endpoints.

### 9.4 Analysis Endpoints

The main analyses will be performed in all subjects who enter the Off-treatment Durability Study Period. It is acknowledged that this population will include participants with varying measures of cough impact and severity as assessed by the ePROs both at the end of the 1-year treatment (ie, Week 52), as well as compared to prestudy baseline (ie, Week 0).

The primary metric of treatment durability will compare the ePRO measurement after 12 weeks off-treatment, to the measurement at Week 52 (ie, immediately prior to treatment discontinuation), and will specifically seek to describe the proportion of participants who either fail to maintain their treatment response, or who maintain treatment response.

One way to describe “failure to maintain the response” for a given ePRO, as an example, is that either the 12 weeks off-treatment measurement is decreased by at least X% of the Week 52 response, or the participant needs treatment for cough. The actual threshold would be based on considerations about clinically important differences and real-world data experiences. The definition will be specific to each ePRO.

In addition, the data will be explored to examine the impact of on-treatment response to MK-7264 on the outcome measures described above. Specifically, the on-treatment measurement (defined as the difference in the Week 52 measurement compared to Week 0) will be categorized using different threshold definitions of “response”, and the subsequent off-treatment ePRO measurement in the Off-treatment Durability Study Period will be explored as a function of the on-treatment response.

One way to describe the “on-treatment response” for VAS, as an example, is that a participant has a Week 52 measurement at least X-mm lower than the Week 0 measurement. The definition will be specific to each ePRO.

The final details about the analysis endpoints, as well as other aspects of the analyses, will be documented in an Off-treatment Durability Study Period memo, separate from the treatment period supplemental SAP, to be finalized before the completion of the Off-treatment Durability Study Period.

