### **8.2.2.7 Patient Global Impression of Change Questionnaire**

Participants will be asked to rate the change in their chronic cough compared to the start of the study using the PGIC with response options ranging from “very much improved” to “very much worse”.

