### 9.6.1 Statistical Methods for Efficacy Analyses

For each ePRO separately, the proportion of participants who maintain treatment response during the 12-week off-treatment period will be estimated and the associated 95% CI will be calculated using the Clopper-Pearson method.

Time-to-event endpoints will be summarized using Kaplan-Meier estimates.

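### No Week 52 PGIC is scheduled in P030, so the stated primary durability metric cannot be formed for that endpoint

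*Combined protocol and SAP*

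**What the plan says.** All references are to the combined protocol and SAP.

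- **Endpoint list.** Appendix 7, Section 3, gives the first exploratory objective as "Objective: To evaluate the off-treatment durability after 1 year of treatment with MK-7264, over the course of 3 months off treatment". Its endpoints are Cough Severity VAS, LCQ, CSD, PGIC and EQ5D-5L. Appendix 7, Section 8.2.2, names the same five as measures to be completed according to the "SoA above: CSD, Cough Severity VAS, LCQ, PGIC, and EQ5D-5L".
- **Primary durability metric.** Appendix 7, Section 9.4, says this metric "will compare the ePRO measurement after 12 weeks off-treatment, to the measurement at Week 52".
- **Scope of the analysis.** Appendix 7, Section 9.6.1: "For each ePRO separately, the proportion of participants who maintain treatment response during the 12-week off-treatment period will be estimated", with a Clopper-Pearson 95% interval. No instrument is exempted.
- **On-treatment response.** Appendix 7, Section 9.4, adds that "the on-treatment measurement (defined as the difference in the Week 52 measurement compared to Week 0) will be categorized" using several thresholds.
- **What PGIC asks.** Under Section 8.2.2.7 of the main protocol, participants "rate the change in their chronic cough compared to the start of the study using the PGIC".
- **When PGIC is collected.** The durability schedule (Appendix 7, Section 1.3) marks it at Visit 17 and durability discontinuation only. The main schedule (Section 1.3) marks it at Visit 6 (Week 12), Visit 9 (Week 24) and Main-period discontinuation only.

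**The concern.** The analysis text needs two PGIC values per participant, one at the end of treatment and one after 12 weeks off it. The schedules supply only the second. Because PGIC refers back to study start, a single Visit 17 rating does not separate the cases that the metric is meant to separate. A moderate improvement at Visit 17 fits a response fully kept, and it also fits a larger Week 52 improvement partly lost. A rating of no improvement fits complete loss, and it also fits a participant who had not improved at Week 52. Appendix 7, Section 9.4, itself expects entrants to differ in their status at Week 52, so this ambiguity will arise.

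At stake is one planned analysis for one of five endpoints. If nothing is done, a substitute would have to be chosen late.

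**Working it through.** No power or sample-size calculation is involved. The check sets the analysis text against the two schedules.

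**1. Off-treatment interval.** Visit 13 is Day 365 and Visit 17 is Day 449. (449 − 365)/7 = 84/7 = 12.0 weeks, which reproduces the plan's 12 weeks. Visit 17 is therefore the off-treatment side of the metric and Visit 13 is the Week 52 side.

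**2. Scheduled values by instrument.**

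| Instrument | Week 0 | Week 52 (Visit 13) | Week 64 (Visit 17) | Week 52 metric |
|---|---|---|---|---|
| LCQ | yes | yes, in both schedules | yes | can be formed |
| EQ5D-5L | yes | yes, in the durability schedule only | yes | can be formed |
| CSD | yes, daily from Visit 1 | yes, daily in the week before Visit 13 | yes, daily to the evening before Visit 17 | can be formed |
| Cough Severity VAS | yes, daily from Visit 1 | yes, daily in the week before Visit 13 | yes, daily to the evening before Visit 17 | can be formed |
| PGIC | none | **none** | yes | **cannot be formed** |

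The CSD and VAS entries come from Sections 8.2.2.2 and 8.2.2.3 of the main protocol and Section 8.2.2 of Appendix 7. For LCQ, a completed Visit 13 questionnaire is also an entry criterion (Appendix 7, Section 5.1, criterion 3).

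**3. Could an earlier PGIC stand in?** The last scheduled on-treatment PGIC is at Week 24 (Day 168).
- To end of treatment: (365 − 168)/7 = 197/7 = 28.1 weeks.
- To Visit 17: (449 − 168)/7 = 281/7 = 40.1 weeks.

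A Week 24 rating is not a Week 52 rating, and the text does not offer it as one. The Main-period discontinuation PGIC does not help either, because criterion 1 for the durability period requires completion of both earlier periods on study intervention.

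**4. On-treatment response.** Section 9.4 of the appendix defines this as Week 52 relative to Week 0. PGIC has neither value, and a rating of change from study start has no natural Week 0 value. Adding Visit 13 would repair the Week 52 to Week 64 comparison but would still leave this definition empty for PGIC.

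**5. The EQ5D-5L contrast.** In the main schedule EQ5D-5L, like PGIC, has no Extension assessment. The durability schedule adds EQ5D-5L at Visit 13 but not PGIC, and gives no reason for the difference.

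**The case against.** **The definitions are still open.** Section 9.4 of the appendix presents its rule for failing to maintain response only as an example, says definitions will be specific to each instrument, and defers final details to a memo. A percentage-loss rule never suited a categorical rating, and collection only at Visit 17 and discontinuation is consistent with a deliberate end-of-period global rating, although the documents do not say so. What stands is that a PGIC-specific definition is needed in any case. But the memo can set thresholds or exempt PGIC; it cannot supply an uncollected value. It need only be final before the period completes. With about 16 months planned for the period and about 3 months per participant, the last Visit 13 falls around month 16 − 3 = 13, so a late memo could follow every Visit 13. The example rule also counts need for cough treatment as failure. That part can be observed without a Week 52 PGIC, but it does not classify participants who take no such treatment.

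**Visit 17 PGIC is still informative.** This stands. It shows whether participants still rate themselves improved over study start after 12 weeks off treatment, and it can be examined against on-treatment response on LCQ, EQ5D-5L, CSD or VAS. What is lost is the within-person PGIC change from Week 52.

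**The period is exploratory.** This also stands. No hypothesis is tested, there is no inferential testing, and the results go into a separate report.

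**A stronger reading on numbers.** A reader might infer that the gap affects all of the approximately 150 participants, especially as Section 2.2.2 describes P027 as similar in most respects. The documents do not support this. The 150 are pooled across P027 and P030, the split may vary, and P027's durability schedule is not included.

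**Conclusion.** The inconsistency is real and confined to PGIC. In P030 the stated Week 52 metric has no scheduled PGIC comparator, so it can be formed for none of the P030 durability participants; their number is not given. Four of the five instruments are unaffected.

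A reader might go further and infer that durability cannot be assessed, or that the trial's main conclusions are touched. Neither follows. The other four instruments and the time-to-event endpoints address durability, Visit 17 PGIC keeps its descriptive value, and no primary, secondary or safety analysis uses a Week 52 PGIC.

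The conclusion rests on the position of the marks in the two PGIC rows. In the durability schedule that row lines up with the LCQ and EQ5D-5L rows above it. In the main schedule its post-baseline marks fall in the same columns as those of SF-12. It also rests on taking the each-instrument wording in Section 9.6.1 of the appendix to include PGIC. If the sponsor did not intend that, the remedy is to say so.

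**What to change.** 1. Add PGIC at Visit 13 in the durability schedule. LCQ and EQ5D-5L are already completed there, and that visit's questionnaires are already activated by entering dates in the vendor portal.
2. State in Section 9.4 of the appendix or in the durability memo that, for PGIC, the Week 52 rating is itself the on-treatment response, since there is no Week 0 value. Define maintained response by PGIC categories at Visit 13 and Visit 17 rather than by percentage loss.
3. For participants already past Visit 13, or if the schedule cannot be changed, state that PGIC is excluded from the Week 52 metric and report Visit 17 PGIC descriptively by arm. Where only some participants have a Week 52 PGIC, give that denominator.

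The cost is one more short questionnaire at an existing visit, one mark in the schedule and a few lines in the memo. The fallback needs only the memo text, at the price of losing the within-person PGIC comparison for those participants.
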